Lay Summary and Keywords Please provide the following information about your study. *Provide a brief lay summary describing this study. (limit 500 words). Pheochromocytoma is a catecholamine (ex. adrenaline) secreting tumor for which the primary treatment is surgical resection. Due to the hormones secreted by the tumor, alpha receptors on peripheral blood vessels are activated, causing constriction of these blood vessels and dangerously high blood pressure. During resection of the tumor, the source of excess hormone secretion is abruptly removed, which can lead to life-threatening blood pressure fluctuations during surgery. Alpha blockers are a class of medication that blocks the alpha receptor on blood vessels. Given preoperatively over a few weeks, these medications negate the effects of the excess hormones secreted by the pheochromocytoma, reducing the frequency and severity of dangerous blood pressure fluctuations intraoperatively and postoperatively. Preoperative alpha blockade is therefore critical to safely perform surgery to resect Phenoxybenzamine, a non-selective alpha blocker, is the most common medication used to alpha block patients prior to pheochromocytoma resection. However, due to increasing drug costs and increased side effects in comparison with selective alpha blockers, there is a renewed interest in studying alternatives to phenoxybenzamine. Selective alpha blockers such as doxazosin are also commonly used to alpha block patients prior to pheochromocytoma resection. Selective alpha blockers are significantly less expensive and are associated with fewer side effects than phenoxybenzamine. Most retrospective studies comparing phenoxybenzamine with selective alpha blockers show no difference in intraoperative blood pressure fluctuations, morbidity, or mortality in pheochromocytoma resection. The purpose of our study is to analyze preoperative, intraoperative, and postoperative outcomes in patients undergoing pheochromocytoma resection. We will compare a prospective group of patients who receive doxazosin (selective) for alpha blockade prior to surgery to a retrospective group of patients who received phenoxybenzamine (non-selective). Outcomes will include postoperative morbidity and mortality, intraoperative hemodynamic instability, quality of life, and cost. *List three to five keywords describing this study (separate the words with commas). The keywords may be used for identifying certain types of studies. pheochromocytoma, alpha blocker, randomized controlled trial * Is this study conducted or supported by HHS (e.g., the National Institutes of Health, Centers for Control and Prevention, etc.)? O Yes O No * Is this study regulated by the Food and Drug Administration (FDA)? O Yes No 4.1 If yes, check all that apply: **Human Drugs Medical Devices Biological Products**

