	Personal identifiers and/or codes linking the data and/or specimens to personal identifiers will be maintained for future research.
	Audio or Video recordings will be transcribed and then destroyed or modified to eliminate the possibility that study participants could be identified.
ı	Photos or Images will be modified to eliminate the possibility that study participants could be identified.
	Restricted use data will be destroyed or returned to the source.
	1.1 If you indicated that personal identifiers will be maintained for future research, provide the following information: a) How the information will be securely handled and stored b) assure confidentiality, and c) who will have access to the identifiers and/or codes. Once the research described in this study is completed, we will destroy the key linking patient names and identifiers to the data used for analysis. The de-identified data or spreadsheet used for analyses will be retained for 1-2 years after the study results are published.
2.0	Describe any additional steps, if any, to be taken to assure that the subjects' identities and any personal identifying information are kept confidential.
ID: IRB	\$17-000048 View: NEW 9.6 - Use of Data and/or Specimens without Direct Contact

This view has been locked by amendment(s)

Warning: Save your work at least every 15 minutes by clicking "Save" or "Continue."

Use of Data and/or Specimens without Direct Contact

You indicated that some or all of the research activities do not involve direct contact with study participants (Section 8.1/item 1.0). Please provide the following information.

1.0 If all of your research activities are without direct contact with study participants, provide the following information:

1.1 Indicate the purpose of the research, specifying the problems and/or hypotheses to be addressed:

The purpose of our study is to analyze preoperative, intraoperative, and postoperative outcomes in patients treated with selective (doxazosin) or non-selective (phenoxybenzamine) alpha blockade prior to pheochromocytoma resection. Outcomes will include postoperative morbidity and mortality, intraoperative hemodynamic instability, quality of life, and cost.

We hypothesize that doxazosin is not inferior compared to phenoxybenzamine in terms of postoperative morbidity and mortality, intraoperative hemodynamic instability, quality of life, and cost.

1.2 Describe the study design and proposed data analyses:

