Given the difficulty in randomizing patients (high cost of phenoxybenzamine has caused a large portion of patients crossing over to the doxazosin arm, resulting in unbalance between the number of patients in each arm), patients who have been pre-treated with doxazosin before pheochromocytoma resection prospectively followed during the course of this study will be compared to a retrospective group of patients who were pre-treated with phenoxybenzamine.

Descriptive statistics including mean, median, standard difference, and frequencies will be calculated for each of the variables measured.

Differences in hemodynamic instability as indexed by specific vital sign parameters, ICU length of stay, inpatient length of stay, morbidity, mortality, cost, and quality of life will be analyzed with t tests or non-parametric tests as appropriate.

1.3 *If you will conduct genetic analysis with specimens, provide your assurance that the results will not be disclosed to subjects or used for clinical care.

Agree	
Not Applicable	

2.0 *Describe specimens and/or data that will be acquired without direct contact with study participants. Complete this item for each type used in the study:

usea in the stu	uy.	
Source	Data and/or Specimens Information	
View UCLA medical records	Data and/or Specimens? Indicate all that apply:	Data
	Indicate whether the data and/or specimens are pre-existing, at the time of this study, and/or if collection will be prospective:	Pre-existing
	Describe the data and/or specimens and indicate the original collection dates:	Electronic medical records from patients undergoing adrenalectomy for pheochromocytoma or paraganglioma from January 1, 2015 to present. Please see item 4.0 for further details on data to be collected from the EMR.
	Indicate the approximate number of data records and/or specimens to be collected:	50
	Will the specimens be used with animals?	No
	If yes, indicate the IACUC Number:	No Value Entered

*If any sources of data and/or specimens are not at UCLA, provide your agreement that the appropriate institutional approvals for release will be obtained (e.g., IRB approval).

Agree

•	
Not Applicable	
	o third parties, please contact the CTSI for directions about additional requirements. sources/pages/third_party
nttps://www.ctsi.ucla.edu/researcher-re	sources/pages/third_party
uttps://www.ctsi.ucla.edu/researcher-re	

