The time required of study subjects will includes time that will be standard for the care of the patient and unrelated to participation of the study. This involves preoperative evaluation by a surgeon (30 minutes) and anesthesiologist (30 minutes), inpatient surgery and routine inpatient postoperative care (average length of inpatient stay 2-3 days), and postoperative follow up (30 minutes).

Additional time required of the study subjects as related to the study would involve 5 questionnaires administered in person or by phone at the time points outlined above, with each administration of the survey taking approximately 5 minutes.

*Statistics and Data Analysis: Describe the proposed statistical procedures or descriptive analyses for the study. If applicable, indicate how the sample size was determined.

Descriptive statistics including mean, median, standard difference, and frequencies will be calculated for each of the variables measured.

This view has been locked by amendment(s)

Warning: Save your work at least every 15 minutes by clicking "Save" or "Continue."

Characteristics of the Study Population

1.0 *Is this an observational or ethnographic study for which the number of participants observed or interviewed cannot be determined in advance.

O Yes O No

- 2.0 If you answered "no" to item 1.0, indicate the maximum number of study participants you hope to enroll: 62
- 3.0 How many participants do you expect you will need to recruit, consent and/or screen to meet the target number above?
- *Indicate the specific inclusion criteria for enrollment of each of the groups of research participants in this study.

 If there are any inclusion criteria based on *gender, pregnancy/childbearing potential, race, ethnicity or language spoken*, explain the nature of and scientific rationale for the inclusions.

 Inclusion criteria include:

(1) Diagnosis of pheochromocytoma or paraganglioma as evidenced by appropriate biochemical evaluation and imaging.

- (2) Surgical resection recommended.
- (3) Patients aged 12 and older.
- *Indicate the specific exclusion criteria for each of the groups of research participants in this study.

 If there are any exclusion criteria based on gender, pregnancy/childbearing potential, race, ethnicity or language spoken, explain the nature of and scientific rationale for the exclusions.

 None.
- 6.0 *How (chart review, additional tests/exams for study purposes, etc.), when and by whom will eligibility be determined?

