Additionally discuss any measures that will be taken to minimize risks. If data are available, estimate (a) the probability that a given harm may occur, (b) its severity, and (c) its potential reversibility. The information provided should be reflected in risks section of the informed consent documents.

If this is an exempt study and there are no risks, indicate N/A. Otherwise, please see the help text. The potential risks of the study include the following:

LOSS OF CONFIDENTIALITY: Although patient identifiers and data will be stored on a secure server with limited access, basic contact information such as the patient's name, address, and telephone number may be at risk if the server is compromised.

STANDARD OF CARE DRUG RISKS: Since both drugs are standardly used to prepare patients for pheochromocytoma surgery, participating in this research study will not expose patients to additional risks beyond what is considered standard of care. Studies comparing phenoxybenazime and doxazosin have mostly shown no difference in blood pressure fluctuations during surgery.

Risk/Benefit Analysis

4.0 *RISKS/BENEFIT ANALYSIS: Indicate how the risks to the participants are reasonable in relation to anticipated benefits, if any, to participants and the importance of the knowledge that may reasonably be expected to result from the study:

Current retrospective data suggest that selective alpha blockade is as effective as non-selective blockade in addition to being less costly and associated with less frequent adverse effects. A randomized controlled trial demonstrating this will result in societal cost savings and increased health related quality of life in patients undergoing pheochromocytoma resection.

Alternatives

5.0 *Indicate the alternatives to participating in this study.

Check all that apply.

	All types	s of studies - Choose not to participate in the study
		ntervention Studies - Receive standard of care instead of participating in the study
		ntervention Studies - Medication, device, or other treatment is available off study
		lot Applicable (e.g., study of existing data)
⊢	Other	The state (sign) state of stat
	0	
	5.1	If "other" was selected, specify.
	5.2	If this is a clinical/intervention study:
		Describe the standard of care or activities at UCLA (or study
		site) that are available to prospective participants who do not enroll in this study. If not applicable to your study, state not

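### Section 9.6 hypothesizes non-inferiority but plans only tests of difference, so on morbidity, mortality and hemodynamic instability the expected null result could not support it

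*Combined protocol and SAP*

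**What the plan says.** Section 9.6 item 1.1 gives the hypothesis: "We hypothesize that doxazosin is not inferior compared to phenoxybenzamine in terms of postoperative morbidity and mortality". The same sentence goes on to name hemodynamic instability during surgery, quality of life and cost.

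Item 1.2 of the same section describes the current design, in which prospectively followed doxazosin patients are compared with a retrospective phenoxybenzamine group. It promises descriptive statistics and then one inferential method. The objects of analysis are "Differences in hemodynamic instability as indexed by specific vital sign parameters, ICU length of stay, inpatient length of stay, morbidity, mortality", with cost and quality of life, and the method is that "morbidity, mortality, cost, and quality of life will be analyzed with t tests or non-parametric tests as appropriate". Neither item gives a margin, a confidence-interval rule or a one-sided level.

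The visible text of the Statistics and Data Analysis item in section 10.1 is a single sentence: "Descriptive statistics including mean, median, standard difference, and frequencies will be calculated for each of the variables measured". The interim safety look in section 15.2 is also a test of difference (chi square, threshold P < 0.05).

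On the expected direction, the Lay Summary (section 2.2) says: "Most retrospective studies comparing phenoxybenzamine with selective alpha blockers show no difference in intraoperative blood pressure fluctuations, morbidity, or mortality in pheochromocytoma resection". Risks & Benefits item 2.0 expects doxazosin to be clinically equivalent on morbidity and mortality, cheaper, and possibly better for quality of life. Item 4.0 of that section adds: "Current retrospective data suggest that selective alpha blockade is as effective as non-selective blockade in addition to being less costly".

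**The concern.** A difference test starts from equality and asks whether the data contradict it. A significant result in favor of doxazosin would support the hypothesis, and one against doxazosin would count against it. A non-significant result does neither: it is compatible with equality, with a small deficit and, in a small study, with a large one. Non-inferiority needs a stated largest tolerable deficit and an interval that excludes it.

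For cost, and possibly for quality of life, the documents expect doxazosin to do better, so a difference test can serve. The gap is in morbidity, mortality and hemodynamic instability, where the documents expect no difference. There the stated analysis offers no route from the expected result to the hypothesized conclusion. If P>0.05 were taken as support, a smaller or noisier data set would supply that support more easily, and nothing would limit the chance of missing a material safety deficit.

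**Working it through.** **The plan's own figure.** Section 11.1 gives a target of 62 and an enrollment rate of 85%. 62 / 0.85 = 72.94, rounded up to 73, as stated. The 62 itself cannot be reproduced, because the supplied text gives no effect size, SD, event rate, power or margin.

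**The two items side by side.** Item 1.1 claims that doxazosin is not inferior. Item 1.2 tests whether the groups differ. Rejecting equality in doxazosin's favor supports item 1.1; failing to reject it does not. This step needs no numbers.

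**How often a real deficit would go unflagged (illustration).** The documents give no arm sizes for the current comparison, so two splits are assumed:
- 31:31, the target of 62 divided equally.
- 62:50, doxazosin first, using the target of 62 and the roughly 50 records in section 9.6 item 2.0. The documents do not say that all 50 are phenoxybenzamine patients.

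A two-sided 0.05 level is also assumed, since the only stated threshold is the interim one.

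*Continuous outcome, t test.* The standard error in SD units is SE = √(1/n₁ + 1/n₂), the non-centrality is d/SE, and the chance of P>0.05 is the non-central t probability between ±t(0.975, n₁+n₂−2).

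| Split | SE | Critical t | P>0.05 if 0.3 SD worse | 0.5 SD worse | 0.8 SD worse |
|---|---|---|---|---|---|
| 31:31 | 0.254 | 2.000 | 79% | 51% | 13% |
| 62:50 | 0.190 | 1.982 | 65% | 26% | 1% |

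The 95% interval half-width is critical t × SE: 2.000 × 0.254 = 0.508 SD and 1.982 × 0.190 = 0.377 SD. A result just short of significance against doxazosin therefore has an interval reaching a deficit of about twice that, 1.02 SD or 0.75 SD.

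The rule also rewards less data. At a true 0.5 SD deficit, P>0.05 occurs in 74% of studies with 15 per arm, 51% with 31 and 21% with 62.

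*Binary outcome, Fisher's exact test.* Item 1.2 names no test suited to event rates, so Fisher's test is an assumption. Summing the binomial probabilities of every table with P ≥ 0.05:

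| True rate, phenoxybenzamine → doxazosin | 31:31 | 62:50 |
|---|---|---|
| 5% → 10% | 98% | 88% |
| 5% → 15% | 90% | 66% |
| 10% → 20% | 90% | 74% |

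For rare events, a non-significant result is close to guaranteed whether or not the rate has doubled.

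**The case against.** The strongest objection is that the missing margin may not be missing from the plan. The section 10.1 statistics item asks for procedures and for the basis of the sample size. Its visible text is one sentence and then breaks to another form page, and a target of 62 appears later with no derivation. Attachments such as the study-variables file were not supplied. This stands as a limit: a reader might infer that the whole plan lacks a margin, but the documents support only that none appears in the supplied text. It does not remove the mismatch between items 1.1 and 1.2 of section 9.6, which read as complete.

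A second objection is that no decision rule is misused. A reader might infer that the investigators will declare non-inferiority from P>0.05, but no sentence says so. The Lay Summary and the risk/benefit text show which result is expected; they are not analysis rules, and the latter also speaks of a randomized trial and bundles effectiveness with cost and adverse effects. The harm is therefore conditional. What remains is that the plan states no reading of the result it thinks most likely.

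A third is that the phrase may be loose wording for a general expectation. If so, a wording change settles it. A reader might also take its absence from the Specific Aims in section 10.1 as a sign that the claim was dropped. The text there may be cut as well, so nothing can rest on it.

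Finally, confounding from the retrospective comparator may be the larger threat to validity. That is a separate problem, and it does not make a null test evidence of non-inferiority.

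**Conclusion.** The concern holds for section 9.6 and for three of the hypothesized outcomes: morbidity, mortality and hemodynamic instability. On these the stated analysis cannot support the stated hypothesis if the expected null result occurs. A reader might extend this to every outcome, but for cost, and possibly quality of life, the documents expect a difference in doxazosin's favor, which a difference test can show.

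The size is illustrative only. With 31:31 and 62:50, a true 0.5 SD deficit passes without significance in 51% and 26% of studies, and a true doubling from 5% to 10% in 98% and 88%. The splits, effect sizes, event rates, significance level and Fisher's test are assumptions. The logical point does not depend on them.

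Severity: should fix. Confidence is high for the mismatch within section 9.6 and moderate that no margin exists elsewhere.

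**What to change.** Revise section 9.6 items 1.1 and 1.2 to:
- state the aim as estimation;
- report each doxazosin-minus-phenoxybenzamine difference with a 95% confidence interval, exact for stroke, myocardial infarction and death;
- state that no conclusion of non-inferiority will be drawn from P>0.05.

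This changes wording and reporting only and needs no more patients.

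Only if a non-inferiority claim is wanted for an outcome, fix a justified margin in that outcome's units before outcomes are compared, and require the two-sided 95% interval to exclude it. Because the comparator records already exist, the justification should not draw on their results. If the section 10.1 statistics item or an attachment already holds a margin, cite it in item 1.2.

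The margin route needs a feasibility check. With an assumed 0.5 SD margin, no true difference and one-sided 0.025, power is about 49% at 31:31 and 74% at 62:50; 80% power needs about 64 per arm. For an event rate of 5% in both groups, n per arm = (1.96 + 0.8416)² × 2 × 0.05 × 0.95 / margin². That is 75 for a 10-point margin and 299 for a 5-point margin.

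The downside of either route is that the study may have to report an inconclusive result. Neither removes confounding from the retrospective comparator, since an interval accounts for sampling error only.

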INTRAOPERATIVE PROTOCOL. Intraoperative hemodynamic monitoring will be conducted in the standard fashion, and a phenylephrine dose response curve will be generated by titration with phenylephrine to estimate the ED30 and therefore the effectiveness of the blockade. Surgery will proceed in the standard fashion. Times of induction, tumor manipulation, and adrenal vein ligation will be recorded. Vasopressors will be used at the discretion of the anesthesiologist.

POSTOPERATIVE PROTOCOL. Patients will be taken to the PACU for routine postoperative care. Admission to the surgical ICU will be performed at the discretion of the attending anesthesiologist and surgeon.

QUALITY OF LIFE / DRUG ADVERSE EFFECTS. Data regarding patient health related quality of life and drug adverse effects will be collected at five time points pre-blockade, post-blockade, and postoperatively at 3 months, 6 months, and 1 year. Health related quality of life data will be assessed utilizing the Short Form-36. Patients will be queried to specific adverse effects such as nasal congestion, headaches, palpitation, as well as their frequency and level of distress caused. Surveys will be complete in person during routine encounters or over the phone.

COST. Preoperative drug costs will be determined using the average wholesale price per unit multiplied by the number of units taken by the patient. Enrollment of the patient in Medicare and Medicare part D will be noted. Data regarding out of pocket drug costs will be collected. Inpatient costs will be calculated utilizing patient charges and the application of a charge to cost ratio.

4.1	* Will you be providing results of any experimental tests that
	are performed for the study?

o	Not Applicable
0	No
0	Yes - Complete Items 4.1.1 and 4.1.2

- 4.1.1 You indicated in Item 4.1 that the research involves experimental tests. Please describe the tests, provide a rationale for providing participants with the experimental test results and explain what, how and by whom participants and their health care provider will be told about the meaning, reliability, and applicability of the test results for health care decisions.
- 4.1.2 Will tests be performed by a Clinical Laboratory Improvement Amendments (CLIA) approved lab?

 Yes No

$^{5.0}$ *Indicate how much time will be required of the subjects, per visit or contact, and in total for the study.

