- (1) Cost. The cost of prescription drugs in the United States is increasing, with the cost of some drugs increasing by over 1000% in the last decade.[1] Currently, the maximum listed wholesale price per unit of phenoxybenzamine is \$197.79 in contrast to \$1.42 for doxazosin[2]. In our anecdotal experience, an increasing number of patients are unable to afford phenoxybenzamine for preoperative alpha blockade prior to pheochromocytoma resection. As current studies show no differences in morbidity and mortality between selective and non-selective alpha blockade prior to pheochromocytoma resection, doxazosin is likely to represent a clinically equivalent option associated with significant cost savings.
- (2) Quality of life. Phenoxybenzamine is a long-acting, non-competitive, non-selective alpha blocker that crosses the blood brain barrier, causing centrally mediated side effects including headaches and sedation that limit the medication's tolerability. Patients who receive doxazosin in comparison to phenoxybenzamine prior to pheochromocytoma resection less frequently experience postural hypotension, nasal stuffiness, and headache.[3] In addition to being cost effective, doxazosin may also be associated with increased health related quality of life while receiving alpha blockade.

Overall, current retrospective data suggest that selective alpha blockade is as effective as non-selective blockade in addition to being less costly and associated with less frequent adverse effects. A randomized controlled trial demonstrating this will result in societal cost savings and increased health related quality of life in patients undergoing pheochromocytoma resection.

- [2] http://micromedex.com/Portals/1/Assets/AWP%20Policy_Oct%202014.pdf

Risks

*Indicate the potential risks/discomforts, if any, associated with each intervention or research procedure.

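### Intraoperative instability is compared on vital signs alone, although discretionary vasopressors alter those vital signs and their use is not a compared outcome

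*Combined protocol and SAP*

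**What the plan says.** Section 9.6, item 1.2 compares doxazosin patients followed prospectively with a retrospective phenoxybenzamine group. It takes "Differences in hemodynamic instability as indexed by specific vital sign parameters", together with ICU stay, inpatient stay, morbidity, mortality, cost and quality of life, and states that these "will be analyzed with t tests or non-parametric tests as appropriate". The visible text does not name the vital sign parameters or their thresholds, and the list contains no measure of vasoactive drug use.

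The intraoperative protocol in section 10.1, item 4.0 says: "Vasopressors will be used at the discretion of the anesthesiologist". On what is captured during surgery it says: "Times of induction, tumor manipulation, and adrenal vein ligation will be recorded". It names no vasopressor agent, dose or duration as a data item. It also plans that "a phenylephrine dose response curve will be generated by titration with phenylephrine to estimate the ED30", as a gauge of how well the blockade works.

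The hypothesis in section 9.6, item 1.1 reads: "We hypothesize that doxazosin is not inferior compared to phenoxybenzamine in terms of postoperative morbidity and mortality, intraoperative hemodynamic instability". No margin is given. Section 9.6, item 2.0 expects about 50 existing records from 2015 onward and points to item 4.0 for the data to be taken from them. A Study variables attachment is listed in section 10.1, item 1.0 but is not reproduced.

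**The concern.** A vasopressor given for low pressure raises the pressure that the outcome measures. A patient who needed a large infusion and a patient who needed nothing can leave the same pressure record. The background in section 10.1 names low pressure after tumor removal as a main hazard of this operation, so the masking falls on a central part of the outcome.

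The two drugs also act differently. The Risks & Benefits section, item 2.0 states: "Phenoxybenzamine is a long-acting, non-competitive, non-selective alpha blocker". A different need for rescue is therefore plausible, although the documents do not say which group would need more.

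The design adds a second route. One group comes from past charts and the other from prospective follow-up. If anesthetic practice differed between them, the recorded pressures could differ or agree for reasons unrelated to the alpha blocker. The planned t or non-parametric tests have no term for this. What is at stake is whether similar recorded pressures can be read as similar stability.

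**Working it through.** **1. The plan's own figure.** The only sample-size figure with visible inputs is in Characteristics of the Study Population, item 6.0: 62 / 0.85 = 72.9, rounded up to 73. It reproduces, but does not bear on this point. No alpha, power, SD, effect size or margin for instability is visible, so the effect of masking cannot be computed from the plan. Everything in steps 3 to 5 is an assumed illustration.

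**2. The text side by side.**

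| Element | Vital signs | Vasoactive drug use |
|---|---|---|
| In the compared outcomes (9.6, item 1.2) | Yes | No |
| Named as recorded (10.1, item 4.0) | Standard monitoring, three event times | Not named |
| Governed by a stated rule | Standard monitoring | Left to discretion |

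**3. Binary illustration.** Let p be the proportion who would become hypotensive without rescue, and f the fraction of recorded episodes that rescue prevents. The recorded rate is p(1 − f). Assume 50% in one group and 30% in the other, a true difference of 20 points.

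- f = 0.50: 0.50 × 0.50 = 0.25 and 0.30 × 0.50 = 0.15, a difference of 10 points.
- f = 0.70: 0.50 × 0.30 = 0.15 and 0.30 × 0.30 = 0.09, a difference of 6 points.
- f = 0.90: 0.50 × 0.10 = 0.05 and 0.30 × 0.10 = 0.03, a difference of 2 points.

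If practice differs, the reverse can happen. With a true 50% in both groups but f = 0.50 in one and 0.90 in the other, the recorded rates are 25% and 5%: a 20-point difference from practice alone.

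**4. Continuous illustration.** Assume an unrescued nadir pressure with means of 90 and 80 mmHg, SD 15 and rescue below 90 that corrects a fraction r of the deficit. The mean deficit below 90 is 15 × 0.399 = 6.0 in the first group, and 10 × 0.7475 + 15 × 0.3194 = 12.3 in the second. The observed mean difference is therefore 10 − r × (12.3 − 6.0) = 10 − 6.3r.

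| r | Observed difference by formula (mmHg) | Simulated (mmHg) | t-test power, 31 v 31 | t-test power, 50 v 62 |
|---|---|---|---|---|
| 0 | 10.0 | 9.9 to 10.0 | 74% | about 93% |
| 0.50 | 6.9 | 6.8 to 6.9 | 72% | 92% |
| 0.75 | 5.3 | 5.3 to 5.4 | 68% | 90% |
| 0.90 | 4.3 | 4.4 | 59% | 85% |

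The group sizes are assumptions: an even split of 62, or 50 records against 62 enrolled. The difference in the proportion rescued stays at about 25 points throughout (0.7475 − 0.50). Power falls less than the mean difference because rescue also narrows the spread. A Fisher test on rescue had power of 43% to 44% (31 v 31) or about 75% (50 v 62), below the t test on pressures. In this illustration the rescue outcome adds information that pressures lose, rather than a more powerful test.

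**5. Direction.** With equal f, the recorded difference is (1 − f) times the true one, so it keeps its sign and shrinks. If doxazosin is truly worse, shrinkage helps a false non-inferiority claim. If phenoxybenzamine is truly worse, it hides an advantage of doxazosin.

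**The case against.** **Direction.** A reader might infer that the plan is tilted toward its own hypothesis. The documents do not support that. The only directional evidence, in Risks & Benefits, item 2.0, is that doxazosin patients have postural hypotension less often. That evidence is preoperative and, if anything, points the other way. Vasopressors also mask only low pressure, and the text is silent on drugs for high pressure.

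**Blinding.** A reader might infer that unblinded anesthesiologists steer the outcome. No blinding is described, and section 9.6, item 1.2 reports that the "high cost of phenoxybenzamine has caused a large portion of patients crossing over to the doxazosin arm", so knowledge of the drug is likely. It remains an inference, and the masking does not need it.

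**Unseen material.** The Study variables attachment may define the parameters and list pressor data, and the Statistics and Data Analysis item in section 10.1 may be cut short. The quoted list comes from a form item headed for work without patient contact, so it may not be the complete analysis list. This limits confidence. Even so, collecting a field does not put it into a comparison, and this is the only comparison list visible.

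**Size.** Rescue given after a low reading leaves that reading on record, so high prevention fractions need not apply. The modest power loss in step 4 shows how much depends on the assumptions. This objection stands in full.

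**Remedy.** Folding rescue into a composite would put a discretionary act inside the endpoint and could reach a ceiling. Requiring both components to show non-inferiority cannot be applied without a margin. The phenylephrine for the ED30 curve would count as rescue unless excluded. Nothing shows that the curve was done in the retrospective group, so including it could create a false group difference. These objections stand and shape the fix.

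**Conclusion.** The point holds in a limited form. On the visible plan, instability is compared by vital signs only, vasopressors are discretionary, and no comparison of their use is stated. Recorded pressures can therefore understate a true difference in either direction, and differing practice between the two cohorts can add to the distortion. It favors a false non-inferiority conclusion only if doxazosin patients need more rescue.

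The size is unknown. The illustrations range from a modest loss of power to near-complete loss of a 20-point difference, all on assumed inputs. The shrinkage rests on rescue following low pressure and working similarly in both groups. The study can proceed, but its instability result should not be read without rescue data.

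**What to change.** In section 9.6, item 1.2, and in the Statistics and Data Analysis item of section 10.1:

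- Add intraoperative vasoactive drug use for pressure control as a separate outcome compared between groups: any use, cumulative amount and infusion time, each before and after adrenal vein ligation.
- Abstract it from the anesthesia record by one written rule in both groups.
- Exclude the phenylephrine given for the ED30 curve from this outcome, and exclude the pressures it produces from the vital-sign outcome.
- State that the two results will be interpreted together and that similar stability will not be claimed from vital signs alone.

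If the Study variables attachment already lists these fields, only the comparison and the exclusion need to be added. The cost is a few more abstraction fields and one more outcome. That outcome itself reflects discretionary practice, so it must be shown separately and read with that in mind. No change to patient care is proposed.
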